3.1 Statistical Hypotheses

Sequential hypotheses testing with Bonferroni-based multiplicity control over the overall Type I error rate at 5% for 2-sided tests and 2.5% for 1-sided tests for the co-primary endpoints and then the co-secondary/secondary endpoints will be performed in order as defined in each supplemental cohort. The margins of 1-sided non-inferiority tests on the neutralizing antibody titers to the COVID-19 variant of interest in the study intervention group are a 1.5-fold rise in geometric mean titers (GMTs) and -10% for seroresponse rates, compared to that in the comparator group. The margin of 1-sided superiority tests on the post-booster neutralizing antibody titers to the COVID-19 variant of interest in the study intervention group is a 2-fold rise in GMT compared to pre-booster.

3.1.1 Evaluation of Booster candidates in Supplemental Cohorts 1 and 2

For Supplemental Cohorts 1 and 2 in younger adults (18-55 years of age), 3 booster candidates in total: CoV2 preS dTM-AS03 (D614) in Supplemental Cohort 1 and CoV2 preS dTM-AS03 (B.1.351) and CoV2 preS dTM-AS03 (D614 + B.1.351) in Supplemental Cohort 2, share the same Comparator Group of SARS-CoV-2-naïve adults, unvaccinated, 18-55 years of age, who will receive the CoV2 preS dTM-AS03 (D614) vaccine as a primary series of 2 injections given 21 days apart, for hypothesis testing. To control for multiple testing, the Bonferroni adjustment will be applied to maintain overall type I error at 0.025 one-sided (0.025/3 for each comparison of booster candidate).

[figure not shown]
For the CoV2 preS dTM-AS03 (D614) booster candidate, there are 2 co-primary endpoints to be hypotheses tested with one-sided alpha 0.025/3 in participants primed with the Pfizer/BioNTech vaccine. If the primary objectives are met, then 2 conditional secondary endpoints will be hypotheses tested with one-sided alpha 0.025/3 applying the sequential testing strategy in participants primed with the CoV2 preS dTM-AS03 (D614) vaccine in the Original Phase II Cohort. If the primary objectives in the Pfizer/BioNTech vaccine primed and conditional secondary objectives in the CoV2 preS dTM-AS03 (D614) vaccine primed are both met, then 2 conditional secondary endpoints will be hypotheses tested with one-sided alpha 0.025/3 applying the sequential testing strategy in participants primed with an mRNA vaccine. If the primary objectives in the Pfizer/BioNTech vaccine primed, conditional secondary objectives in the CoV2 preS dTM-AS03 (D614) vaccine primed, and conditional secondary objectives in the mRNA vaccine primed are all met, then 2 conditional secondary endpoints will be hypotheses tested with

one-sided alpha 0.025/3 applying the sequential testing strategy in participants primed with an adenovirus vector vaccine. If the primary objectives in the Pfizer/BioNTech vaccine primed and conditional secondary objectives in the CoV2 preS dTM-AS03 (D614) vaccine primed, the mRNA vaccine primed, and adenovirus vector vaccine primed are all met, then 1 conditional secondary endpoint on seroresponse will be hypotheses tested at one-sided alpha 0.025/3 in each Pfizer/BioNTech primed, CoV2 preS dTM-AS03 (D614) primed, mRNA primed, and adenovirus vector primed sequentially by applying the sequential testing strategy.

For the CoV2 preS dTM-AS03 (B.1.351) booster candidate, there are 2 co-primary endpoints to be hypotheses tested at 0.025/3 one-sided level in participants primed with the Pfizer/BioNTech vaccine. If the primary objectives are met, then 2 conditional secondary endpoints will be hypotheses tested at 0.025/3 one-sided level in participants primed with an mRNA vaccine applying the sequential testing strategy. If primary objectives and conditional secondary objectives are both met, then 1 conditional secondary endpoint (GMT) will be hypothesis tested with one-sided alpha 0.025/3 in participants primed with the Pfizer/BioNTech vaccine applying the sequential testing strategy. If the primary objectives, conditional secondary objectives, and conditional secondary objective on GMT are all met, then 1 conditional secondary endpoint on seroresponse will be hypothesis tested at one-sided alpha 0.025/3 in each Pfizer/BioNTech primed and mRNA primed sequentially by applying the sequential testing strategy.

For the bivalent booster candidate, there are 4 co-primary endpoints on both D614G and B.1.351 variants (if the SARS-CoV-2 D614G variant remains in circulation globally based on reports from authorities [eg, WHO]) or 2 co-primary endpoints on the B.1.351 variant to be hypotheses tested at 0.025/3 one-sided level in participants primed with the Pfizer/BioNTech vaccine. If the primary objectives are met, then 4 conditional secondary endpoints on both D614G and B.1.351 variants (if the SARS-CoV-2 D614G variant remains in circulation globally based on reports from authorities [eg, WHO]) or 2 conditional secondary endpoints on the B.1.351 variant will be hypotheses tested at 0.025/3 one-sided level in participants primed with an mRNA vaccine applying the sequential testing strategy. If primary objectives and conditional secondary objectives are both met, then 1 conditional secondary endpoint on GMT will be hypothesis tested with one-sided alpha 0.025/3 in participants primed with the Pfizer/BioNTech vaccine applying the sequential testing strategy. If the primary objectives, conditional secondary objectives, and conditional secondary objective on GMT are all met, then 2 conditional secondary endpoints on seroresponse for both D614G and B.1.351 variants (if the SARS-CoV-2 D614G variant remains in circulation globally based on reports from authorities [eg, WHO]) or 1 conditional secondary endpoint on seroresponse for B.1.351 variant will be hypotheses tested at one-sided alpha 0.025/3 in each Pfizer/BioNTech primed and mRNA primed sequentially by applying the sequential testing strategy.

Figure 3.1: Multiplicity adjustment strategy using Bonferroni and sequential testing method in Supplemental Cohort 1 and Supplemental Cohort 2

Note:

- i. H1, H2 and H3 corresponding to the hypothesis testing of CoV2 preS dTM-AS03 (D614) in Supplemental Cohort 1, CoV2 preS dTM-AS03 (B.1.351) in Supplemental Cohort 2, and CoV2 preS dTM-AS03 (D614 + B.1.351) in Supplemental Cohort 2.
- ii. H3 of CoV2 preS dTM-AS03 (D614 + B.1.351) in Supplemental Cohort 2 will include hypothesis testing of D614G (H3d, dotted circled ones in Figure 9.1) (if the SARS-CoV-2 D614G variant remains in circulation globally based on reports from authorities [eg, WHO]) and B.1.351 (H3b).
- iii. H(=1,2,3b, or 3d)₁ corresponding to the hypothesis testing of co-primary endpoints. H(=1,2,3b, or 3d)_(=2,3,4) corresponding to the hypothesis testing of conditional secondary endpoint(s).
- iv. H(=2 or 3b)₃ corresponding to the hypothesis testing of conditional secondary endpoints for superiority claim on B.1.351.
- v. H(=1,2,3b, or 3d)_(=s1,s2,s3,s4) corresponding to the hypothesis testing of conditional secondary endpoint(s) for non-inferiority claim on seroresponse.
- vi. H(=1,2,3b, or 3d)_{(=1,2,3,4)1} corresponding to the hypothesis testing of non-inferiority. H(=1,2,3b, or 3d)_{(=1,2,3,4)2} corresponding to the hypothesis testing of superiority.

The hypothesis testing strategy of each booster candidate is as follows:

- Supplemental Cohort 1 – CoV2 preS dTM-AS03 (D614)
 - Overall type 1 error at 0.025/3 one-sided level will be maintained
 - a) 2 co-primary endpoints will be hypothesis tested in participants primed with the Pfizer/BioNTech vaccine at one-sided 0.025/3 alpha level
 - b) A sequential testing strategy will be applied for the 2 conditional co-secondary endpoints in participants primed with the CoV2 preS dTM-AS03 (D614) vaccine in the Original Phase II Cohort if the 2 co-primary endpoints in participants primed with the Pfizer/BioNTech vaccine at one-sided 0.025/3 alpha level is achieved
 - c) A sequential testing strategy will be applied for the 2 conditional co-secondary endpoints in pooled participants primed with an mRNA vaccine if the 2 co-primary endpoints in participants primed with the Pfizer/BioNTech vaccine and 2 conditional co-secondary endpoints in participants primed with the CoV2 preS dTM-AS03 (D614) vaccine in the Original Phase II Cohort at one-sided 0.025/3 alpha level are both achieved
 - d) A sequential testing strategy will be applied for the 2 conditional co-secondary endpoints in pooled participants primed with an adenovirus vector vaccine if the 2 co-primary endpoints in participants primed with the Pfizer/BioNTech vaccine, 2 conditional co-secondary endpoints in participants primed with the CoV2 preS dTM-AS03 (D614) vaccine and 2 conditional co-secondary endpoints in pooled participants primed with an mRNA vaccine at one-sided 0.025/3 alpha level are all achieved
 - e) A sequential testing strategy will be applied for the 1 conditional secondary endpoint on seroresponse in participants primed with the Pfizer/BioNTech vaccine, in participants primed with the CoV2 preS dTM-AS03 (D614) vaccine, in pooled participants primed with an mRNA vaccine, and in pooled participants primed with an adenovirus vector vaccine at one-sided 0.025/3 alpha level will be tested sequentially if the 2 coprimary endpoints in participants primed with the Pfizer/BioNTech vaccine, 2 conditional co-secondary endpoints in participants primed with the CoV2 preS dTM-AS03 (D614) vaccine, 2 conditional co-secondary endpoints in pooled participants primed with an mRNA vaccine, 2 conditional co-secondary endpoints in pooled participants primed with an adenovirus vector vaccine at one-sided 0.025/3 alpha level are all achieved
- Supplemental Cohort 2 – CoV2 preS dTM-AS03 (B.1.351)
 - Overall type I error at 0.025/3 one-sided level will be maintained
 - a) 2 co-primary endpoints will be hypothesis tested in participants primed with the Pfizer/BioNTech vaccine at one-sided 0.025/3 alpha level
 - b) A sequential testing strategy will be applied for the 2 conditional co-secondary endpoints in pooled participants primed with an mRNA vaccine if the

2 co-primary endpoints in participants primed with the Pfizer/BioNTech vaccine at one-sided 0.025/3 alpha level is achieved

- c) A sequential testing strategy will be applied for the 1 conditional secondary endpoint of superiority testing on B.1.351 in participants primed with the Pfizer/BioNTech vaccine if the 2 co-primary endpoints in participants primed with the Pfizer/BioNTech vaccine and 2 co-secondary endpoints in pooled participants primed with an mRNA vaccine at one-sided 0.025/3 alpha level are both achieved
- d) A sequential testing strategy will be applied for the 1 conditional secondary endpoint on seroresponse in participants primed with the Pfizer/BioNTech vaccine at one-sided 0.025/3 alpha level if the 2 co-primary endpoints in participants primed with the Pfizer/BioNTech vaccine, 2 conditional co-secondary endpoints in pooled participants primed with an mRNA vaccine, and 1 conditional secondary endpoint on GMT at one-sided 0.025/3 alpha level are all achieved
- e) A sequential testing strategy will be applied for the 1 conditional secondary endpoint on seroresponse in pooled participants primed with an mRNA vaccine at one-sided 0.025/3 alpha level if the 2 coprimary endpoints in participants primed with the Pfizer/BioNTech vaccine, 2 conditional co-secondary endpoints in pooled participants primed with an mRNA vaccine, 1 conditional secondary endpoint on GMT, and 1 conditional secondary endpoint on seroresponse in participants primed with the Pfizer/BioNTech vaccine at one-sided 0.025/3 alpha level are all achieved

- Supplemental Cohort 2 – CoV2 preS dTM-AS03 (D614 + B.1.351)
- Overall type I error at 0.025/3 one-sided level will be maintained
- The objectives will be evaluated on the pseudovirus neutralizing titers to the B.1.351 variant and the pseudovirus neutralizing titers to the D614G variant (if the SARS-CoV-2 D614G variant remains in circulation globally based on reports from authorities [eg, WHO]). The objective would be considered to be achieved if both variants or only B.1.351 variant are met based on the D614G variant circulation situation for whether testing on D614G variant is needed or not
 - a) 2 co-primary endpoints for pseudovirus neutralizing titers against B.1.351 and 2 co-primary endpoints for pseudovirus neutralizing titers against D614G (if the SARS-CoV-2 D614G variant remains in circulation globally based on reports from authorities [eg, WHO]) will be hypothesis tested in participants primed with the Pfizer/BioNTech vaccine at one-sided 0.025/3 alpha level
 - b) A sequential testing strategy will be applied for the 2 conditional co-secondary endpoints for pseudovirus neutralizing titers against B.1.351 and 2 conditional co-secondary endpoints for pseudovirus neutralizing titers against D614G (if the SARS-CoV-2 D614G variant remains in circulation globally based on reports from authorities ([eg, WHO]) in pooled participants primed with an mRNA vaccine if the 4 co-primary endpoints both on the B.1.351 variant and the D614G

variant (if the SARS-CoV-2 D614G variant remains in circulation globally based on reports from authorities [eg, WHO]) or 2 co-primary endpoints on the B.1.351 variant in participants primed with the Pfizer/BioNTech vaccine at one-sided 0.025/3 alpha level are achieved

- c) A sequential testing strategy will be applied for the conditional secondary endpoint of superiority testing on B.1.351 in participants primed with the Pfizer/BioNTech vaccine if the primary objectives in participants primed with the Pfizer/BioNTech vaccine and conditional secondary objectives in pooled participants primed with an mRNA vaccine at one-sided 0.025/3 alpha level are both achieved
- d) A sequential testing strategy will be applied for the 2 conditional secondary endpoints on seroresponse for both B.1.351 and D614G variants if the SARS-CoV-2 D614G variant remains in circulation globally based on reports from authorities (eg, WHO) or 1 conditional secondary endpoint on seroresponse only for B.1.351 variant in participants primed with the Pfizer/BioNTech vaccine at one-sided 0.025/3 alpha level if the primary objectives in participants primed with the Pfizer/BioNTech vaccine, conditional secondary objectives in pooled participants primed with an mRNA vaccine, and conditional secondary objective on GMT in participants primed with the Pfizer/BioNTech vaccine at one-sided 0.025/3 alpha level are all achieved
- e) A sequential testing strategy will be applied for the 2 conditional secondary endpoints on seroresponse for both B.1.351 and D614G variants if the SARS-CoV-2 D614G variant remains in circulation globally based on reports from authorities (eg, WHO) or 1 conditional secondary endpoint on seroresponse only for the B.1.351 variant in pooled participants primed with an mRNA vaccine at one-sided 0.025/3 alpha level if the primary objectives in participants primed with the Pfizer/BioNTech vaccine, conditional secondary objectives in pooled participants primed with an mRNA vaccine, conditional secondary objective on GMT in participants primed with the Pfizer/BioNTech vaccine, and conditional secondary objective on seroresponse in participants primed with the Pfizer/BioNTech vaccine at one-sided 0.025/3 alpha level are all achieved.

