3.1.1.1 A Pooled Primary Series Cohort as Supplemental Cohort 2 Comparator Group

As the number of authorized and/or approved COVID-19 vaccines increases, promptly enrolling the planned 515 naïve participants into the Comparator Group shared by Supplemental Cohorts 1 and 2 may become unattainable. In order to maintain sufficient target power for Supplemental Cohort 2 hypothesis testing, in case of a substantial shortfall in numbers of Comparator Group participants, a pooled primary series cohort with a sample size of at least 464 (a 10% dropout rate from 515) evaluable participants may be planned to serve as the Comparator Group for Supplemental Cohort 2.

Participants in this pooled primary series cohort will be added from 2 potential sources, in the following order:

1. All SARS-CoV-2-naïve participants contemporaneously enrolled in Supplemental Phase III Cohort 1
2. Eligible participants from studies involving the same investigational CoV2 preS dTM-AS03 vaccine which include:
 - a) VAT00002 Original Phase II Cohort participants, enrolled at US sites, who received the 10 µg antigen dose of the CoV2 preS dTM-AS03 vaccine and are included in the PPAS Naïve-D01+D22 population
 - b) VAT00008 participants enrolled at US sites who received the CoV2 preS dTM-AS03 (D614) and are included in the IAS Naïve-D01+D22 population

Evaluable participants will be pooled in sequence from the above sources. Three scenarios for pooling data will be applied, as applicable:

Scenario A: If the number of evaluable Supplemental Phase III Cohorts Comparator Group participants is ≥ 260 , which corresponds to a power of at least 70% for Cohort 2 primary objectives, Scenario A will be applied. This scenario is only applicable to VAT00002 Supplemental Phase III Cohort participants and there is no pooled primary series.

The evaluable participants in the Supplemental Cohorts Comparator Group will provide sufficient sample size, or despite a shortfall the Sponsor determines that the Supplemental Comparator Group would not be augmented with additional data sources. In this scenario, only the contemporaneously enrolled Supplemental Cohorts Comparator Group will be included in hypothesis testing, with no additional population sources.

Since no pooled Comparator Group is needed, exploratory sensitivity analysis for the pooled population will not be performed. The main analysis on the full population will be performed as planned.

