3.2 Sample Size Determination

3.2.1 Supplemental Phase III Cohorts 1 and 2

A Bonferroni adjustment is used to control the overall type I error rate at 0.025 one-sided in Supplemental Cohorts 1 and 2, so each comparison of the Booster Group with the Comparator Group will be performed at one-sided significance level of 0.00833 (0.025/3). No alpha-splitting within hypothesis testing of co-primary endpoints. Assumed attrition rate of Primary Vaccination Group is 10% and Booster Group is 3% (it is anticipated that attrition to 14 days post booster will be limited and smaller than the attrition to D36 in the Comparator Group). Other assumptions for sample size calculation are as follows:

- The PsVN Std Dev is around 0.65 for primary vaccination at D36 and around 1.0 for booster vaccination at D22 on \log_{10} scale base on immunogenicity data obtained from Monogram for the corresponding assay
 - Note: The assumption of the standard deviation of the assay is based on the final interim data of D614G on the PPAS Naïve-D01+D22 at D36 and FAS NonNaïveD01 at D22 from VAT0002 Original Phase II Cohort in participants 18-55 years of age.
- For the primary and secondary objectives in terms of GMT non-inferiority against the comparator (using the D614G titers elicited by the comparator as the benchmark), the ratio of group GMT margin is 1/1.5, the assumed true ratio of group GMT for D614 containing vaccines (comparing D614G titers in both booster vaccine and priming comparator) is 1.5 (this is informed by preliminary interim data from VAT0002 Original Phase II Cohort, indicating titers generally higher in the non-naïve individuals after a single dose, compared to the titers in naïve individuals after 2 doses); and the assumed true ratio of group GMT for the B1.351 variant-containing vaccines (comparing B.1.351 titers in variant-containing vaccines versus D614G titers in the comparator D614 vaccine) is 1 (this is assumed in the absence of data).

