Conditional Secondary Objectives (Type I error: 0.00833)	Adenovirus vector primed CoV2 preS dTM-AS03 (D614) Booster Group (N=150)			
 Non-inferiority: 94% Superiority: 99.1% Overall: 93.2%
Conditional Secondary Objective (Type I error: 0.00833)	Pfizer primed CoV2 preS dTM-AS03 (D614) Booster Group (N=215)	Non-inferiority on seroresponse 
 Assumed true Comparator Group seroresponse rate: 99% Assumed actual difference between Booster and Comparator Groups: -2.5% Margin: -10% 		95.3%
Conditional Secondary Objectives	CoV2 preS dTM-AS03 (D614)primed CoV2 preS dTM- AS03 (D614)			98.9%

(Type I error: 0.00833)	Booster Group (N=270)		
Conditional Secondary Objective (Type I error: 0.00833)	mRNA primed CoV2 preS dTM-AS03 (D614) Booster Group (N=290)		99.4%
Conditional Secondary Objective (Type I error: 0.00833)	Adenovirus vector primed CoV2 preS dTM-AS03 (D614) Booster Group (N=150)		78.2%
Cohort 2 CoV2 preS dTM-AS03 (B.1.351) Booster Group			
Primary Objectives (Type I error: 0.00833)	Pfizer primed CoV2 preS dTM-AS03 (B.1.351) Booster Group (N=515)	
 Assumed true ratio of group GMT: 1 Margin: 1/1.5 Std Dev (booster): 1.0 Std Dev (comparator): 0.65 	
 Assumed true ratio: 5 Margin: 2 Std Dev (booster): 1.0 
 Non-inferiority: 80.5% Superiority: > 99.9% Overall: 80.5%
Conditional Secondary Objectives (Type I error: 0.00833)	mRNA primed CoV2 preS dTM-AS03 (B.1.351) Booster Group (N=590)		
 Non-inferiority: 84.5% Superiority: > 99.9% Overall: 84.5%
Conditional Secondary Objective on B.1.351 variant (Type I error: 0.00833)	Pfizer primed CoV2 preS dTM-AS03 (B.1.351) booster group (N=515)	
Superiority on ratio of group GMT (GMT against B.1.351 vs comparator GMT against B.1.351)
 
 Assumed true ratio of group GMT: 3 Margin: 1.5 Std Dev (booster): 1.0 Std Dev (comparator): 0.65 	> 99.9%
Conditional Secondary Objective on seroresponse (Type I error: 0.00833)	Pfizer primed CoV2 preS dTM-AS03 (B.1.351) booster group (N=515)	
Non-inferiority on seroresponse
 
 Assume true comparator group seroresponse rate: 99% Assumed actual difference between booster and comparator group: -2.5% Margin: -10% 	> 99.9%

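### The fixed 0.025/3 level for each booster candidate is valid but needlessly conservative: passing on the alpha of a fully rejected chain would raise Cohort 2 primary power at the same family-wise error

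*SAP*

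**What the plan says.** Section 3.1 announces "Sequential hypotheses testing with Bonferroni-based multiplicity control over the overall Type I error rate at 5% for 2-sided tests and 2.5% for 1-sided tests". Section 3.1.1 names three candidates that share one comparator group: D614 in Cohort 1, and B.1.351 and the bivalent vaccine in Cohort 2. It applies Bonferroni to hold the overall one-sided error at 0.025, with "0.025/3 for each comparison of booster candidate".

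The level is repeated for each candidate: "Overall type 1 error at 0.025/3 one-sided level will be maintained" for D614, and "Overall type I error at 0.025/3 one-sided level will be maintained" for each of the two Cohort 2 candidates. Every listed step uses 0.025/3, including the last seroresponse step of each sequence. Section 3.2.1 says that "each comparison of the Booster Group with the Comparator Group will be performed at one-sided significance level of 0.00833 (0.025/3"), and sections 3.1.1.2 and 3.1.1.3 fix every decision on a two-sided 98.3% interval.

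No sentence passes alpha from a completed sequence to another. Figure 3.1 is not reproduced in the text available, but its title and notes mention only Bonferroni and sequential testing.

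On power, Table 3.1 gives "Non-inferiority: 80.5" (percent) for each Cohort 2 primary on B.1.351. Section 3.1.1.1 accepts at least 260 evaluable comparators without pooling, "which corresponds to a power of at least 70% for Cohort 2 primary objectives".

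**The concern.** Once a candidate's entire sequence has been rejected, the 0.025/3 assigned to it has nothing left to protect. Under the stated rule it lapses. A Bonferroni-based graph with weights of one third each lets it move to the candidates still open: 0.0125 each after one sequence is complete, and 0.025 for the last after two. Control of the family-wise error at 0.025 holds under any dependence, so the shared comparator is no obstacle.

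The loss falls where power is shortest. The Cohort 2 primaries are planned at 80.5%, and at about 70% if Scenario A is applied at its lower edge. The same holds at the end of the Cohort 1 sequence, where the seroresponse step for adenovirus-primed participants is planned at 78.2%.

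**Working it through.** **Inputs** (section 3.2.1 and Table 3.1). SD on the log10 scale is 1.0 for booster and 0.65 for comparator. The margin is 1/1.5. The true GMT ratio is 1 for the Cohort 2 B.1.351 primary and 1.5 for D614 titers. Planned N is 515 and 515, with attrition of 3% and 10%, so 515 × 0.97 ≈ 500 booster and 515 × 0.90 ≈ 464 comparator participants are evaluable.

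**Error budget.** 3 × 0.025/3 = 0.025. The interval level is 1 − 2 × 0.00833 ≈ 98.3%.

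**Step 1: reproduce the plan's power.** The effect is log10(1) − log10(1/1.5) = 0.1761. The standard error is √(1.0²/500 + 0.65²/464) = √(0.002000 + 0.000911) = 0.05395. The ratio of effect to standard error is 0.1761/0.05395 = 3.264. A one-sided two-sample t-test with Welch degrees of freedom at 0.00833 gives 80.6%, against 80.5% stated. The other GMT non-inferiority powers in Table 3.1 also reproduce: computed/stated 98.8/98.7, 99.7/99.7, 99.8/99.8 and 94.2/94 for Cohort 1, and 84.5/84.5 for the pooled mRNA step of Cohort 2.

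**Step 2: same test at the levels a graph would allow.** These are conditional values, given that other sequences are complete.

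| Evaluable comparators | 0.025/3 | 0.0125 (one other sequence complete) | 0.025 (both others complete) |
|---|---|---|---|
| 464 | 80.6% | 84.6% | 90.3% |
| 260 | 70.0% | 75.1% | 83.2% |

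**Step 3: how often alpha is released.** The stated step powers of the Cohort 1 sequence multiply to 0.987 × 0.996 × 0.998 × 0.932 × 0.953 × 0.989 × 0.994 × 0.782 = 0.67 if treated as independent. The conditional values therefore overstate the average gain.

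**Step 4: unconditional gain.** All three sequences were simulated with a shared comparator, at least 200,000 runs per setting. Alpha was released only after a whole sequence was rejected and was split equally. Seroresponse was taken as independent of GMT, and fold-rise as independent of the between-group comparison.

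| Quantity | Present rule | With transfer |
|---|---|---|
| Cohort 2 primary, each arm, 464 comparators | about 81% | about 87% |
| The same, Cohort 1 sequence as only donor | about 81% | about 83% |
| Cohort 2 primary, each arm, 260 comparators | about 70% | about 78% |
| Whole Cohort 1 sequence, 464 comparators | about 68% | about 81% |

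The last row sets the Cohort 1 seroresponse steps at their Table 3.1 powers. Simulating the Wilson score intervals directly gives about 70% to 85% for that row and 87% to 88% for the first row with transfer. Most of the Cohort 2 gain comes from the other Cohort 2 candidate, whose sequence is completed about 79% of the time under the present rule.

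**The case against.** The strongest reply is that nothing here is wrong. The three levels sum to 0.025, the rule is applied consistently, Table 3.1 is built on it, and plain Bonferroni across candidates judged separately is a legitimate choice. That stands, and it makes the change optional.

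A reader might go further than the documents allow in three ways.

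- *That type I error is uncontrolled.* It is controlled; the rule errs only on the conservative side.
- *That Cohort 2 primaries would be tested at roughly 64% to 70% power with 200 to 260 comparators.* Those figures are what the contemporaneous comparator alone would give. In that range Scenario B makes a pooled comparator the main analysis, section 3.1.1.1 plans that pool at no fewer than 464 evaluable participants, and the contemporaneous-only comparison becomes an exploratory sensitivity analysis. The low-power case that remains is Scenario A near 260, or a sponsor decision not to augment.
- *That the gain is the step from 80.6% to 90.3%.* That needs both other sequences to be complete; the average gain is about 6 to 7 points.

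Two practical objections also stand. The Cohort 1 sequence cannot finish on Cohort 1 data: its second step uses participants primed with the study vaccine and boosted with D614 in Cohort 2 (Table 1.2). Their planned number of 270 is an estimate, and the Cohort 1 interim trigger in section 3.5 does not require their data. And the fixed 98.3% intervals have a merit of their own: for one primary comparison per candidate, joint coverage is at least 1 − 3 × (0.05/3) = 95%. Intervals whose level depends on results do not give that.

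**Conclusion.** The point holds as one of efficiency. The present rule is valid, and a graph with the same starting weights never rejects less at the same family-wise error. The size is about 6 to 7 points of power for each Cohort 2 primary with 464 comparators (only 2 to 3 if the Cohort 1 sequence is the sole donor), about 8 points with 260, and about 13 points for completing the Cohort 1 sequence.

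The conditional values of 84.6% and 90.3% rest only on the SAP's SDs, margin, attrition and true ratio of 1. The unconditional figures rest also on the independence assumptions in the simulation, on the Table 3.1 seroresponse rates, and on about 270 study-vaccine-primed participants being available. No reason for forgoing the transfer is given in the SAP; a wish for one fixed interval level would be a fair one. Optional improvement.

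**What to change.** In section 3.1.1 and Figure 3.1, before the first interim database lock, state that:

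1. when every hypothesis in one candidate's sequence is rejected, its alpha passes equally to the remaining candidates (0.0125 one-sided each, then 0.025 for the last);
2. a sequence tested at an earlier lock may be retested at its raised level after a later lock, on the same primary-analysis data;
3. whether the bivalent sequence includes D614G is fixed before its data are unblinded, so that a complete sequence is defined;
4. the Cohort 1 sequence releases alpha only once the study-vaccine-primed participants boosted in Cohort 2 have been analysed;
5. decision intervals follow the local alpha (98.3%, 97.5% or 95% two-sided), with the 98.3% interval always reported alongside.

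Cohort 1 testing can still start at 0.025/3 on its own timetable. The cost is a few sentences, a revised figure and interval levels that depend on results; no participants are added and no rejection is lost. The downside to name in the SAP is that the decision intervals no longer give joint coverage across the three candidates.
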